10.3.2 Randomized Cohort – Primary Efficacy Endpoint

The primary efficacy endpoint is the difference in patency grade of the FSO between the treatment and control sides at Day 30 as determined by an independent, blinded sinus surgeon based on the centralized video-endoscopy review. Patency of the FSO will be assessed endoscopically by probing with a 3-mm olive-shaped frontal sinus suction tip (“suction tip”) and will be analyzed using the paired t-test.

For each subject, the difference in patency grade of the FSO between the treatment and control sides will be calculated and then averaged across all subjects. The difference in patency grade for a given subject will be set as missing if one of the FSO is unable to be viewed or graded.

The primary efficacy hypothesis is that mometasone furoate (MF) from the UP Drug-Coated Device will significantly increase the patency grade on the treatment side compared to control. The statistical test will be paired t-test where the difference in patency grade between treatment and control sides is determined.

The relevant null and alternative hypotheses for this primary efficacy endpoint are:

- $H_0: \mu = 0$
- $H_1: \mu \neq 0$

where μ is the mean difference in the FSO patency grade between the treatment and control sides at Day 30. The study will be considered successful if there is a statistically significant difference in the mean patency grade in favor of the UP Drug-Coated Device.

Although the alternative hypothesis is specified as two-sided, only a statistically significant difference in patency grade favoring treatment sides will constitute evidence of effectiveness. The two-sided α for this test is 0.05 (or one-sided α of 0.025).

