16.3 Analysis of Primary Endpoints

PK cohort

The primary efficacy endpoint is the number of successful balloon dilations, which will be reported with descriptive statistics. The left and right sides of each subject will be considered independent, and each subject is expected to contribute up to 2 observations. The study will be considered successful if $\geq 80\%$ of attempted FSO are dilated successfully with no USADE related to the investigation device. A successful FSO dilation is one in which the physician has inserted the UP Drug-Coated Device into the targeted FSO, followed by 2 consecutive, complete inflations of the balloon.

Continuous data from the plasma MF, plasma cortisol and 24-hour urinary cortisol concentrations will be expressed using descriptive statistics, including but not limited to, means, standard deviations, medians, ranges and, where appropriate, coefficient of variation (%).

Randomized cohort

The primary efficacy endpoint is the difference in the patency grade between treatment sides at Day 30 as determined by an independent, blinded sinus surgeon based on the centralized video-endoscopy review.

The primary efficacy endpoint will be analyzed using the paired t-test.

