17.3 Blinding

17.3.1 Randomization

Randomization assignment will be stratified by site, will follow a blocked scheme with blocks of varying sizes, and will be performed using the envelope method. After subjects meet the study entry criteria, have been anesthetized, and final eligibility confirmed, site personnel will open the assigned randomization envelope for that particular subject.

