9 STATISTICAL METHODS

9.1 Randomization

Eligible subjects in the randomized cohort will have their sinus sides randomly assigned to receive the UP Drug-Coated Device in one FSO (treatment side) while the contralateral FSO (control side)

will receive the UP Control Device. The ratio of left to right FSO assignments will be 1:1. The randomization scheme will be generated by a biostatistician consultant and the randomization envelopes will be assembled by an in-house clinical research associate. The randomization scheme will be stratified by each clinical center. To maintain blinding of study personnel to the treatment assignment, the treatment and control devices will be designated with a letter such as Device C and Device D. The information inside the randomization envelope will indicate which FSO side receives which device letter with no information regarding the treatment or control device (e.g., Device C – LEFT, Device D – RIGHT).

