9.4.2 Randomized Cohort

The sample size was calculated based on the difference in the patency grade at Day 30 between the treatment and control sides with the following assumptions:

- Expected mean difference of 0.5 between the treatment and control sides in patency grade
- A SD of 1.1 for side-to-side difference in the patency grade of the FSO
- Target power of $\geq 90\%$
- Type I error rate of $\alpha = 0.05$, 2-sided

A mean difference in patency grade of 0.5 between the treatment and control sides favoring treatment sides was considered clinically meaningful. Based on standard formulas for a paired t-test, a sample size of 53 subjects provides at least 90% power to detect a difference of 0.5 in mean patency grade between treatment sides. Assuming up to 25% of subjects with non-evaluable data on one or both sides, additional 17 subjects will be enrolled for a total of 70 subjects in the randomized cohort.

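### The primary paired t-test leaves out the randomised side (left or right); it is valid, but one prespecified side term would recover precision at almost no cost

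*SAP*

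**What the plan says.** On allocation, SAP section 9.1 states "The ratio of left to right FSO assignments will be 1:1" and "The randomization scheme will be stratified by each clinical center". Protocol section 17.3.1 adds that assignment "will follow a blocked scheme with blocks of varying sizes"; the SAP does not mention blocks.

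On analysis, protocol section 16.3 says "The primary efficacy endpoint will be analyzed using the paired t-test". SAP section 10.3.2 repeats this ("The statistical test will be paired t-test where the difference in patency grade between treatment and control sides is determined") and forms the estimate as a simple mean: the difference "between the treatment and control sides will be calculated and then averaged across all subjects". A subject's difference is set to missing if either ostium cannot be viewed or graded.

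No primary, secondary or sensitivity analysis has a left/right term. SAP section 10.2 summarises baseline by treatment side, not by left and right. SAP section 10.5 tests for a site effect and considers adjustment for baseline characteristics only if that test is significant.

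**The concern.** Let L be the average left-minus-right difference in Day 30 grade that would exist without any drug effect, for example from anatomy or from operator handedness. A subject with the drug-coated device on the left contributes effect + L, and one with it on the right contributes effect − L. The design balances the two kinds of subject, so L largely cancels from the mean. The paired t-test does not know this and counts the spread between the two groups as random error. The trial therefore controls a factor by design and gives the benefit away in the analysis.

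At stake are a confidence interval wider than it need be and some power, on the primary endpoint and on the three paired t-tests among the four label-claim endpoints in SAP section 10.6. In addition, if the evaluable pairs end up uneven between left and right assignment, L no longer cancels fully in that dataset.

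**Working it through.** **Inputs from the documents.** SAP section 9.4.2 gives the effect ("Expected mean difference of 0.5 between the treatment and control sides in patency grade"), the SD ("A SD of 1.1 for side-to-side difference in the patency grade of the FSO"), two-sided alpha 0.05, 53 evaluable pairs, and up to 25% non-evaluable, which gives 70 enrolled. L is not given; 0, 0.3 and 0.5 grade are assumed.

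**The plan's own figure.** For a paired t-test with n = 53, the noncentrality is (0.5/1.1) × √53 = 3.31 on 52 degrees of freedom. Power is 90.1%, so the stated 53 reproduces.

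**Model.** D = effect + L·s + e, with s = +1 if the drug-coated device is on the left and −1 if on the right. With balanced sides, the variance that the paired t-test sees is Var(e) + L². A model with a side term sees Var(e) only. The SAP does not say whether its SD of 1.1 includes L, so both readings are shown.

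**Standard error, balanced pairs.**
- If 1.1 is the total SD, the ratio of unadjusted to adjusted SE is 1.1/√(1.21 − L²): 1.039 at L = 0.3 and 1.123 at L = 0.5.
- If 1.1 excludes L, the ratio is √(1.21 + L²)/1.1: 1.037 at L = 0.3 and 1.098 at L = 0.5.

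**Power by simulation** (35 left and 35 right randomised, 17 pairs lost at random, 53 analysed; values approximate):

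| L | Reading of 1.1 | Paired t-test | With side term |
|---|---|---|---|
| 0 | either | 90.1% | 90.0% |
| 0.3 | total SD | 90.7% | 92.0% |
| 0.5 | total SD | 92.0% | 95.4% |
| 0.3 | excludes L | 88.5% | 90% |
| 0.5 | excludes L | 85.5% | 90% |

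Under the total-SD reading, unadjusted power rises with L because the near-balance makes the mean more stable than the t-test's own SE implies.

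**Type I error.** Under the total-SD reading, the two-sided error of the paired t-test is a little over 4% at L = 0.3 and a little over 3% at L = 0.5. With the side term it is about 5%.

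**Point estimate.** Given the realised split, the unadjusted mean shifts by L × (n_left − n_right)/n. At 30:23 the factor is (30 − 23)/53 = 0.13, so the shift is 0.04 grade at L = 0.3 and 0.07 at L = 0.5, against an SE of 1.1/√53 = 0.15. With 17 of 70 pairs lost at random from 35:35, a split of 30:23 or worse in either direction has probability about 9%. Averaged over the randomisation, the simulated estimate is 0.500 for a true 0.5 at every L tried.

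**The case against.** The strongest reply is that nothing here is broken. The paired t-test is prespecified, agrees between protocol and SAP, and is the test on which the sample size rests. Its type I error does not exceed nominal, so a positive result cannot be false for this reason. All of that stands.

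L also has no source in the documents. At 0.5, where the gain becomes visible, it equals the whole assumed treatment effect. Entry criteria make the sides similar (both ostia at grade 0 or 1, Lund-Mackay score at least 1 on each side, bilateral ethmoidectomy), and both sides follow the same dilation steps with balloons of the same dimensions. This stands too, and it is why the gain is given as a range that starts at nil.

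A reader might infer that ignoring side biases the treatment estimate. The documents do not support that. If losses do not depend on which side received drug, the estimate is unbiased over the randomisation; only a shift conditional on the realised split remains. Nothing in the plan suggests assignment-dependent loss. The 30:23 example is also unfavourable, although the 9% assumes an exact 35:35 start. With up to 15 sites for 70 subjects (fewer than 5 each on average), incomplete blocks could make such splits more frequent: roughly one trial in six to one in five if blocks of 2/4 or 4/6 are assumed. Block sizes are not given.

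Finally, one common term removes only a left-right difference shared across sites. Handedness effects that differ between operators would partly cancel in that term and stay in the error. This is a real limit of the remedy.

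**Conclusion.** The point holds as an inexpensive gain in efficiency, not as the correction of an invalid or biased test. The assigned side is randomised and blocked but used in no analysis, so any common left-right difference is left in the error. The gain in power is nil at L = 0, about 1.3 points at L = 0.3 and about 3.4 points at L = 0.5 if 1.1 is the total SD. If 1.1 excludes L, the side term restores about 1.5 and 4.5 points, and without it the trial falls below its 90% target. These figures rest on an assumed L, on one L shared by all sites, on normal errors, and on loss of 17 of 70 pairs unrelated to assignment. Planned power is at risk only under the second reading of the SD, which the documents neither confirm nor exclude.

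**What to change.** Before database lock, amend SAP section 10.3.2 and protocol section 16.3:

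- Fit a linear model to each subject's treatment-minus-control difference with one centred side term (+1/2 if the drug-coated device was assigned to the left, −1/2 if to the right). Test the intercept as the treatment effect; it equals the unweighted mean of the two assignment-group means.
- Use the same model for the three continuous endpoints in SAP section 10.6.
- Keep the plain paired t-test as a supporting analysis.
- Report the number of evaluable pairs by assigned side.

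The cost is a few sentences of wording and one degree of freedom (90.0% instead of 90.1% power at L = 0). Left-right effects that differ between sites or operators would not be removed. The timing matters because SAP section 9.2 treats any analysis designed after lock as post hoc and exploratory.

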10.3.2.1 Sensitivity Analysis for Steroid and Surgical Interventions

Because the primary efficacy endpoint for the randomized cohort will be determined by the independent blinded sinus surgeon based on review of video-endoscopies taken at Day 30, interventions performed by clinical investigators prior to Day 30 can potentially confound this outcome. Therefore, a sensitivity analysis will be performed to test the robustness of the efficacy conclusion to actual interventions given. Use of clinically necessary high-dose corticosteroids (e.g., oral, parenteral, injection, budesonide or other sinus steroid irrigations/rinses or drops, nebulized steroids administered nasally) or surgical intervention (e.g., repeat balloon dilation or sinus surgery involving dissection of the FSO) during the study will be tabulated.

In this analysis, data imputations will be performed as follows:

- If at Day 7, 14 or Day 21, a clinical investigator indicates on the Endoscopic Scoring Form that the frontal recess/FSO required oral steroids or surgical intervention, and that intervention was actually given, then the grades given by the independent reviewer at Day 30 will be

replaced by the grades given by the clinical investigator at the visit preceding commencement of oral steroids.

- If oral steroids were actually prescribed for reasons other than frontal sinus obstruction, then the grades given by the independent reviewer at Day 30 will be replaced by the grades given by the clinical investigator at the visit preceding commencement of oral steroids.

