16.7 Sensitivity Analysis for the Primary Efficacy Endpoints

Since the primary efficacy endpoint in the randomized cohort is determined by an independent blinded sinus surgeon based on review of video-endoscopies taken at Day 30, interventions performed by clinical investigators prior to Day 30 can potentially confound the primary efficacy outcome. Therefore, a sensitivity analysis will be performed to test the robustness of the efficacy conclusion to actual interventions given. In this analysis, data imputations will be performed as follows:

- If prior to Day 30, a clinical investigator indicates on the Endoscopic Scoring Form that either frontal recess/FSO required oral steroids or surgical intervention, and such intervention was actually given, then the grades given by the independent reviewer will

be replaced by the grades given by the clinical investigator at the visit preceding such intervention.

- If oral steroids were actually prescribed for reasons other than either frontal recess/FSO, then the grades given by the independent reviewer will be replaced by the grades given by the clinical investigator at the visit preceding commencement of oral steroids (prior to Day 30).

Additional sensitivity analysis may be performed to assess the sensitivity of the primary efficacy conclusion to patterns of missing data. This will be detailed in the statistical analysis plan.

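### SAP 10.3.2.1: surgery or repeat dilation without oral steroids triggers replacement of the Day 30 grade, but the rule names no visit to take the replacement from

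*SAP*

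**What the plan says.** SAP 10.3.2.1 gives its reason for the analysis: "interventions performed by clinical investigators prior to Day 30 can potentially confound this outcome". It counts repeat balloon dilation as surgery, stating that "surgical intervention (e.g., repeat balloon dilation or sinus surgery involving dissection of the FSO) during the study will be tabulated".

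The first bullet begins "If at Day 7, 14 or Day 21, a clinical investigator indicates" and applies where "the frontal recess/FSO required oral steroids or surgical intervention, and that intervention was actually given". The reviewer's Day 30 grades are then "replaced by the grades given by the clinical investigator at the visit preceding commencement of oral steroids".

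The second bullet begins "If oral steroids were actually prescribed for reasons other than frontal sinus obstruction" and closes with the same replacement wording.

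Protocol 16.7 describes the same analysis. Its first rule begins "If prior to Day 30, a clinical investigator indicates on the Endoscopic Scoring Form", refers to either side, and says the reviewer's grades will "be replaced by the grades given by the clinical investigator at the visit preceding such intervention". Its second rule covers oral steroids given for other reasons and ends by limiting itself to steroids started before Day 30.

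**The concern.** The first SAP bullet has two triggers and an anchor for only one of them. Protocol 13.2 allows surgical rescue and does not require a course of steroids beforehand, so rescue by surgery alone is an ordinary possibility. For such a subject the SAP orders a replacement and does not say from which visit.

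The gap matters because surgery or repeat dilation can be done on one side only. It can then change the side-to-side difference directly, and that difference is the primary endpoint. This is the analysis meant to show whether the Day 30 conclusion survives rescue treatment. Where the rule is silent, a programmer could keep the reviewer's grade, set the pair to missing, or use the visit before surgery. Those choices can give different results.

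**Working it through.** **Step 1. Apply both texts to each rescue sequence before Day 30.**

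| Rescue given | Source of grade under SAP 10.3.2.1, first bullet | Source under Protocol 16.7, first rule |
|---|---|---|
| Oral steroids only | Visit before steroids | Visit before steroids |
| Surgery or repeat dilation only | None defined | Visit before surgery |
| Surgery, then steroids | Visit before steroids, possibly after surgery | Visit before surgery is available |
| Steroids, then surgery | Visit before steroids | Visit before steroids is available |

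Example of the third row: need is flagged at Day 7, surgery follows, and steroids start after the Day 14 visit. The SAP selects the Day 14 grade, which is post-surgical. The protocol wording reaches the Day 7 grade. The protocol does not say outright which intervention governs when both are given.

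**Step 2. Look for an explanation in the documents.** SAP 3 states that it was prepared from protocol version 7.0. The version 8.0 change list does not mention Section 16.7, so that amendment does not account for the difference. The two SAP bullets end in identical words, which fit the steroid-only second bullet. A drafting slip is a reasonable inference, though not a documented one.

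**Step 3. Compare the remaining wording.**
- Window: the SAP lists Days 7, 14 and 21; the protocol covers any time before Day 30. Those are all the scheduled follow-up visits before Day 30, so the texts differ only for need flagged solely at an unscheduled visit. SAP 8.3 sends unscheduled-visit data to Section 9.2, which has no rule for them. SAP 9.3 says that protocol-specified visits feed the tables and listings, but does not name unscheduled visits.
- Side: the protocol refers to either frontal recess or ostium; the SAP uses the singular.
- Second bullet: the SAP omits the limit to steroids begun before Day 30. It also defines the other reasons against frontal sinus obstruction, where the protocol refers to either frontal recess or ostium.

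**Step 4. Scale.** Inputs from SAP 9.4.2: mean difference 0.5, SD 1.1, two-sided alpha 0.05, 53 evaluable subjects, 70 enrolled. The plan's own figure reproduces: an exact paired t-test with n = 53 has power 90.1%. It is not in dispute.

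- Shift in the mean when one subject's difference moves by one grade: 1/53 = 0.019; 1/70 = 0.014.
- Smallest significant mean = t(0.975, n-1) x 1.1/sqrt(n). For n = 53: 2.0066 x 0.1511 = 0.303. For n = 70: 1.9949 x 0.1315 = 0.262.
- Total movement against treatment needed to lose significance from 0.5: (0.5 - 0.3032) x 53 = 10.4 subject-grades; (0.5 - 0.2623) x 70 = 16.6.
- At two grades per subject: 10.4/2 = 5.2, so 6 of 53 (11%); 16.6/2 = 8.3, so 9 of 70 (13%).

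This holds the SD at 1.1, although replacing grades would also change it.

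**The case against.** The best defence is that the intent is recoverable. Protocol 16.7 gives the right anchor, the analysis is prespecified in both documents, and settling an ambiguous phrase by the protocol's own rule is arguably not designing a new analysis in the sense of SAP 9.2. Interventions are tabulated in any case, so surgery-only rescue would remain visible. All of that is fair and limits the urgency. It does not make the bullet executable as written, and a choice of grade made after lock, with the results in view, is open to dispute.

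A reader might infer that the second bullet lets steroids started after Day 30 overwrite a Day 30 grade, since follow-up runs to Day 60. The bullet read alone allows this, but the opening sentence of the section confines the purpose to interventions before Day 30. The missing limit is a wording omission and not evidence of a different rule.

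A reader might also infer that the SAP wrongly ignores rescue at unscheduled visits. Protocol 16 calls itself a summary ahead of a formal SAP, and a trigger tied to scheduled visits is compatible with SAP 9.3, so it may be deliberate. Protocol 11.3 requires endoscopic grading at unscheduled visits but does not say that the need-for-intervention item is completed there. What stands is a cross-reference in SAP 8.3 that leads to no rule.

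**Conclusion.** The first bullet of SAP 10.3.2.1 is wrong as written: surgery-only rescue, including repeat dilation, has no defined replacement grade, and surgery followed by steroids can yield a post-surgical one. This rests on the text alone and needs no assumption about rates. The other wording differences are real but minor, and belong in the same edit.

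The effect on the result cannot be sized, because no rescue rate is given and the direction is unknown. The figures above are a benchmark under the design values. They suggest that a few affected subjects would not overturn the sensitivity analysis if the planned effect is observed; a smaller effect leaves less room. They do not support any claim of lost power or of a threat to the primary test, its alpha or the sample size.

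**What to change.** Before database lock, amend SAP 10.3.2.1.

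1. First bullet, the necessary change: end it as Protocol 16.7 does, so that the reviewer's Day 30 grades will "be replaced by the grades given by the clinical investigator at the visit preceding such intervention".
2. First bullet, alignment: open it with "If prior to Day 30, a clinical investigator indicates on the Endoscopic Scoring Form" and refer to either side, as the protocol does. If the list of scheduled visits is deliberate, say so and give the reason.
3. Second bullet: restore the limit to oral steroids begun before Day 30, and reconcile the definition of other reasons with the protocol's.
4. SAP 8.3: check whether the reference to Section 9.2 should be to Section 9.3, and make sure that the section cited contains a rule for unscheduled visits.

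Optional clarifications, which go beyond the protocol text, are which intervention governs when both kinds are given and whether a grade taken at the same visit before the intervention counts as the preceding grade. If same-visit grades are allowed, the order of grading and intervention must be checked case by case, because the documents fix that order only for the baseline procedure.

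The cost of items 1 to 4 is SAP wording. Endoscopic grading is already required at scheduled and unscheduled visits, so no new data are needed.

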13.1 Medical Intervention

During study follow-up, INCS sprays will be allowed starting after Day 14 visit, if clinically necessary, for subjects in the randomized cohort and not allowed throughout the 30-day follow-up period for subjects in the PK cohort.

Other corticosteroids (e.g., oral, parenteral, injection, budesonide or other sinus steroid irrigations, rinses or drops, nebulized steroids administered nasally) will not be permitted unless

there is a clinically significant increase or persistence in frontal sinus inflammation occurs, coupled with subject complaint of sinusitis symptoms that cause subject to request medical intervention.

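### The intervention sensitivity analysis names non-oral high-dose steroids but replaces grades only for oral steroids or surgery, so subjects given only the other listed routes keep their Day 30 grade

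*SAP*

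**What the plan says.** Protocol 16.7 gives the reason for the analysis: "interventions performed by clinical investigators prior to Day 30 can potentially confound the primary efficacy outcome". SAP 10.3.2.1 repeats that reason and aims to show whether the efficacy conclusion holds up against what was really given. It then sets out the exposures it has in mind, "Use of clinically necessary high-dose corticosteroids (e.g., oral, parenteral, injection, budesonide or other sinus steroid irrigations/rinses or drops, nebulized steroids administered nasally", together with surgery such as repeat dilation. The instruction for that list is tabulation.

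Replacement of grades has two triggers. The first fires when the investigator records at Day 7, 14 or 21 that "the frontal recess/FSO required oral steroids or surgical intervention, and that intervention was actually given". The second fires when oral steroids were prescribed for some other reason. Protocol 16.7 has the same two triggers, and Protocol 16.6 likewise only records and tabulates the wider list.

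The untriggered routes can occur before Day 30. Protocol 12 and 13.1 bar the other corticosteroids except on clinical need, which 13.1 ties to increased or persistent frontal sinus inflammation with symptoms. Sprays are treated separately: for the randomized cohort, Protocol 13.1 says "INCS sprays will be allowed starting after Day 14 visit, if clinically necessary". They are neither on the SAP 10.3.2.1 list nor among its triggers, and would surface only in the general medication summary of SAP 10.8.

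**The concern.** Within one section, the purpose and the rule do not match. The SAP names several steroid routes as high-dose interventions that could disturb the Day 30 reading, then acts on one of them. A subject given a steroid injection or a budesonide irrigation between Day 14 and Day 30, and nothing else, enters the robustness check with exactly the grades used in the primary analysis.

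The exposure is not incidental to the outcome, because the condition for giving these steroids is inflammation in the frontal sinus. Each subject is also their own control, so steroid that reaches both sides can reduce the difference on which the primary test rests. Someone reading the study report would assume that the check covers the interventions the section lists. As written, it does not.

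**Working it through.** **Step 1: set the list against the triggers.**

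| Exposure before Day 30 | On the SAP 10.3.2.1 list | Trigger | Result in the check |
|---|---|---|---|
| Oral steroid, for the FSO or another reason | Yes | Yes | Grades replaced |
| Surgery, including repeat dilation | Yes | Yes | Grades replaced |
| Parenteral or injected steroid | Yes | No | Tabulated; Day 30 grade kept |
| Steroid irrigation, rinse or drops | Yes | No | Tabulated; Day 30 grade kept |
| Nebulized nasal steroid | Yes | No | Tabulated; Day 30 grade kept |
| Nasal steroid spray after Day 14 | No | No | Day 30 grade kept |

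A subject in one of the last four rows is caught only if oral steroids or surgery were also given.

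**Step 2: look for another analysis that closes the gap.** SAP 10.3.2.2 deals with missing grades only. The evaluable population in SAP 7.2.2 defines major procedural deviations by treatment before consent and treatment of the wrong side, not by steroid use. SAP 10.5 tests differences between sites. The optional extra analysis in Protocol 16.7 concerns patterns of missing data. None of them tests steroid exposure.

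**Step 3: reproduce the plan's own figure.** The inputs, from SAP 9.4.2, are a planned side difference of 0.5 grade, "A SD of 1.1 for side-to-side difference in the patency grade of the FSO", two-sided alpha 0.05 and 53 evaluable subjects. The noncentrality is 0.5/1.1 × √53 = 3.31. On 52 degrees of freedom the paired t-test has 90.1% power (52 subjects give 89.5%), so the planned figure reproduces. It does not measure this gap: any loss of power from added steroid is the same whether or not the sensitivity analysis is widened.

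**Step 4: how much leverage replacement could have (illustration).** Assume 53 pairs, SD held at 1.1 and an observed mean difference of 0.5. The smallest significant mean is t(0.975, 52) × 1.1/√53 = 2.007 × 1.1/7.280 = 0.303. To lose significance, the replaced subjects' differences must fall by (0.5 − 0.303) × 53, about 10.4 grades in total:

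- 5 subjects (9%): 10.4/5, about 2.1 grades each
- 10 subjects (19%): 10.4/10, about 1.0 grade each
- 15 subjects (28%): 10.4/15, about 0.7 grade each

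These numbers of subjects are assumptions, since the documents give no expected use of any of these routes. If added steroid diluted the difference, replacement would tend to move the mean up, not down.

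**The case against.** The narrow trigger may be deliberate. The post-dilation intervention composite in SAP 10.4.1.1 consists of surgery, oral steroids and repeat dilation, and Protocol 13.2 singles out oral steroids and surgery for recording on the case report forms. Sprays fall outside the SAP's high-dose list, and counting permitted spray use as part of the Day 30 result is a legitimate choice. This stands for sprays, although Protocol 13.1 does place them under medical intervention and the SAP gives no reason for omitting them. It does not stand for the injected, parenteral, irrigated and nebulized routes, which the section itself calls high-dose.

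A reader might infer that a weak Day 30 result could not be told apart from dilution by added steroid. That goes too far. SAP 10.4.2.1 already tests the independent reviewer's Day 14 patency grade, a blinded reading taken before sprays are permitted. Medication is also listed and summarised, and investigator patency is analysed through Day 60. None of this is a formal test of dilution, but it is informative.

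A reader might also infer that a positive result is in doubt. Success requires a significant difference favouring the drug-coated side, and steroid reaching both sides would mainly work against that. The documents show no route by which the omission favours the device.

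Finally, a reader might take the omitted routes to be those most likely to affect Day 30. Nothing in either document ranks them above oral steroids, repeat dilation or surgery, which are covered.

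**Conclusion.** The point holds as a mismatch between purpose and rule in SAP 10.3.2.1, shared by Protocol 16.7. Listed high-dose steroid routes other than oral are reported but not tested, and no other planned analysis fills the gap. It should be corrected before database lock, but it does not undermine the primary analysis.

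Its effect on the result cannot be sized from the documents. It depends on how many subjects receive only an untriggered route and on what that does to their side difference; neither is given. It is tempting to attach a loss of power by assuming a usage rate and an attenuation, but no section supports such values and widening the check would recover none of the loss. Under the Step 4 assumptions, a result at the planned effect would lose significance only if replacement lowered many subjects' differences, or a few subjects' differences by a lot. The judgement that steroid would mainly dilute rests on its reaching both sides; the documents do not fix the direction or the size.

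**What to change.** Before database lock, extend the trigger in SAP 10.3.2.1 to every steroid route on its own list started before the Day 30 visit. Replace both sides' grades with those from the last visit before that intervention began. Stating the reference visit this way also covers surgery without oral steroids, for which the SAP currently points to the visit before oral steroids started. Where Day 14 is that visit, say whether the reviewer's or the investigator's grades are used, since both exist.

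As a separate supportive run, treat nasal steroid sprays started between the Day 14 and Day 30 visits as a trigger and use the independent reviewer's Day 14 grades. Otherwise, state why sprays are left out.

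The cost is one or two extra analyses. Protocol 12 already requires start dates for sinus-related medications; confirm that they are also captured when a listed steroid is given for a non-sinus reason. If the change is made after lock, SAP 9.2 would make it post hoc and exploratory.

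There are downsides. Earlier grades stand in for Day 30, and reviewer and investigator grades are mixed. For steroid started before the Day 7 visit, the preceding scheduled visit is baseline, where eligibility requires grade 0 or 1 on each side, so the replaced difference can only be −1, 0 or 1. Under dilution, replacement may move the estimate towards the device. The result should therefore be read beside the primary analysis and not as a conservative bound. No change to the medication rules is proposed.
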